6.3 MEASURES TO MINIMIZE BIAS: RANDOMIZATION AND BLINDING

Each potential participant will be assigned a unique number in the screening process (screening number). This number will be used to identify the participant throughout the study.

Participants who qualify will be randomized in two sequential cohorts. The dose groups of IXT-m200 or placebo will be at a 2:1 ratio in Cohort 1 and, if the interim analysis supports dose escalation, 2:1 in Cohort 2. If the interim analysis supports dose maintenance or reduction, then the sample size will be recalculated. Placebo participants will be combined for analysis at the end of study. Randomization will be stratified by self-reported past-month METH usage at screening (<18 days versus ≥18 days).

Unblinding of treatment assignment during the study is discouraged and should occur only if it is absolutely necessary for the investigator, Medical Monitor, Sponsor, or participant to know what he or she received for safety reasons. If the Sponsor, the investigator, or Medical Monitor deems identification of the study drug to the participant as necessary for the purpose of providing urgent care, the pharmacy will inform the investigator of the assignment, who will notify the Medical Monitor, Sponsor, and participant. The process of unblinding will be appropriately documented in the investigator file. The date and reason for the unblinding must be recorded. When possible, the Medical Monitor and Sponsor should be notified prior to unblinding; otherwise, they must be notified within 24 hours after unblinding.

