1.2. Study Design

InterveXion's protocol M200C-2201 is a Phase 2, double-blind, placebo-controlled, multiple-dose study of the safety and efficacy of monthly intravenous (IV) doses of IXT-m200 in treatment-seeking individuals with METH use disorder. The study was stopped before enrolling Cohort 2. As such, any reference to Cohort 2 in this document no longer applies, but has been retained for reference.

The study consists of two cohorts:

- In Cohort 1, approximately 60 participants will be randomized in a 2:1 ratio to IXT-m200 1.5 g or placebo (saline).
- In Cohort 2, approximately 60 participants will be randomized in a 2:1 ratio to the recommended dose of IXT-m200 or placebo based on the interim analysis at the end of Cohort 1. If the interim analysis recommends maintaining a dose of 1.5 g, then the sample size will be recalculated.

In each cohort, participants will receive either study drug (IXT-m200 at the cohort-specific dose or placebo) at the beginning of Weeks 1, 5, 9, 13, 17, and 21. All participants will also participate in seven sessions of a standardized cognitive behavioral therapy (CBT) program which will be delivered by a trained therapist; the first dose of IXT-m200 or placebo is intended to be given on the same day of initiation of CBT. For Cohort 1, the participants will participate in the CBT sessions during their monthly visits. For Cohort 2, participants will go to the clinic weekly for saliva drug tests and will participate in CBT sessions every two weeks, starting with Week 1. Participants will be followed at monthly intervals through Week 33. Cohort 1 will use app-based assessments to monitor between visits and Cohort 2 will use TLFB to monitor between visits. Schema 1.2 in the protocol displays the schematic of the study design for Cohort 1, and Appendix 1 shows the schedule of events. The first four weeks of treatment will be considered a grace period, designed to accommodate the likelihood that participants will relapse initially and experience the effects of IXT-m200. It further allows participants time to absorb and incorporate some of the skills taught by cognitive behavior therapy. METH use endpoints will be analyzed in the weeks following the grace period.

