2.2. Sample Size Determination

As this is an exploratory Phase 2A study, the sample size was not set to power the study to statistically detect any particular treatment effect. Instead, it was chosen to balance the need to gather sufficient information regarding treatment effect and variability to plan for Phase 3, while not exposing more subjects than necessary to any yet unknown safety concerns.

Still, an assessment of the potential power of the study for statistical testing is provided in Table 4. These estimates assume that cohort 2 (if conducted) receives a different dose of IXT-m200, and provide the power for comparing *each* dose group to placebo. The primary endpoint will be based on Cohort 2, but cohorts may be pooled to perform additional analyses.

Table 4. Minimum detectable difference between *each* IXT-m200 group versus the placebo group

	placebo group								
	Detectable	Examples of detectable differences with varying pooled SD							
Power	difference	20%	25%	30%					
Cohort 1/	Cohort 2 only								
$(n_1 = 40 \text{ vs})$	$s n_2 = 20$)								
0.80	$0.78 \times \text{pooled SD}$	15.6%	19.5%	23.4%					
		(3.1 more weeks)	(3.9 more weeks)	(4.7 more weeks)					
0.85	$0.84 \times \text{pooled SD}$	16.7%	20.9%	25.1%					
		(3.3 more weeks)	(4.2 more weeks)	(5.0 more weeks)					
0.90	$0.90 \times \text{pooled SD}$	18.1%	22.5%	27.1%					
		(3.6 more weeks)	(4.5 more weeks)	(5.4 more weeks)					
Cohorts 1	and 2 pooled								
$(n_1=40 \text{ vs})$	$s n_2 = 40$)								
0.80	$0.63 \times \text{pooled SD}$	12.6%	15.8%	18.9%					
		(2.5 more weeks)	(3.2 more weeks)	(3.8 more weeks)					
0.85	$0.68 \times \text{pooled SD}$	13.6%	17.0%	20.4%					
		(2.7 more weeks)	(3.4 more weeks)	(4.1 more weeks)					
0.90	$0.73 \times \text{pooled SD}$	14.6%	18.3%	21.9%					
		(2.9 more weeks)	(3.7 more weeks)	(4.4 more weeks)					

The detectable differences were calculated in SAS Proc Power using a two-sample t-test assuming equal variance a two-sided 5% alpha. SD = standard deviation.

The literature suggests that dropout rates in the study population may be up to 50% Error! Bookmark not defined, and therefore the analyses will account for missing data.

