4.1.1. Common Statistical Methods and Data Presentations

Descriptive and inferential statistics will summarize results. Unless otherwise indicated, the prespecified efficacy analyses will be conducted using the ITT population. The study will use an overall nominal two-sided Type I error rate of 5%; results will be reported with a two-sided 95% confidence interval (CI) and nominal p-value. For primary and selected secondary and exploratory efficacy outcomes, plots of the cumulative distribution functions (CDFs) will show differences by treatment arm.

Categorical variables will be summarized with the frequency count and percentage of participants with non-missing data. Continuous variables will be summarized using appropriate summary statistics (e.g., the number of non-missing observations, mean, standard deviation (SD), median, 25th and 75th percentiles, minimum, maximum; geometric mean and 95% confidence intervals (CIs) may also be presented, as appropriate).

All summaries will be by treatment group. Tabular presentations will display a separate column for each treatment regimen and graphical summaries will color-code each treatment regimen.

In addition to tabular and graphical summaries, by-participant listings will present all relevant electronic case report form (eCRF) data, sorted by treatment group and participant identifier.

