4.6.1. Main analytical approach

The primary efficacy analysis will use the ITT population and is based on a test of the mean difference between each IXT-m200 group and the placebo group in percent weeks abstinent, as estimated using an analysis of covariance (ANCOVA). The dependent variable in the model is percent weeks abstinent; the independent variables in the model are the following:

- Treatment group assignment (discrete); and
- Stratification level of past-month METH use at screening (discrete).

[figure not shown]
The data for this primary endpoint will have shown efficacy if the test of mean percent weeks abstinent between Week 5 and Week 25 shows nominal statistically significant benefit in any IXT-m200 group relative to the placebo group.

Adjusted means and standard errors for each treatment group and the estimated difference between the groups and associated 95% confidence intervals and two-sided p-values will be reported. A plot of all saliva screen results for each individual subject throughout the study will be provided. Pseudo-R code for the plot is included in Exhibit 2. The data should be divided into subsets based on the value of the saliva test value for methamphetamine, including 'positive', 'negative', 'missed', 'invalid'. If the result of a saliva screen is not one that is listed, the sponsor should be contacted to receive instruction on how to code the value. If a saliva screen test is missed, that week will be imputed assuming the participant is not abstinent. If a participant withdraws from the study, then all weeks following withdrawal will be assumed as not abstinent. For the *n* subjects, each subject should be assigned a value from 1 to *n* for the purpose of plotting. Participants will be grouped by study treatment. An example plot is available in Exhibit 3.

Exhibit 2 Pseudo-R Code for Saliva Screen Data Plot

```
points(neg placebo$DAY,neg placebo$SUBJIDN,col=rgb(0.2,0.7,0.9,1),pch=17,cex=1)
points(pos placebo$DAY,pos placebo$SUBJIDN,col=rgb(1,0.5,0,1),pch=19,cex=1)
points(miss placebo$DAY,miss placebo$SUBJIDN,col=rgb(1,0.5,0,1),pch=4)
points(inv placebo$DAY,inv placebo$SUBJIDN,col=rgb(1,0.5,0,1),pch=5)
par(mar=c(5,1,4,2))
plot(NA,NA,xlim=c(0,175),ylim=c(0,50),xlab='Study Day',ylab=',main='IXT-M200 Saliva
Screen Results',
    yaxt='n',xaxt='n')
axis(1, at=seq(0, 175, by=7))
axis(2, at=seq(0.50,by=5))
for(i in 0:15){
 polygon(c(14*i+.5,14*i+7.5,14*i+7.5,14*i+.5), c(-5,-
5,75,75),col=rgb(0,0,0,025),border=rgb(0,0,0,025))

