The difference in percentage of days abstinent from stimulants will be compared in each IXT-m200 group versus the placebo group using a t-test. For each comparison, the point estimate and 95% confidence intervals for the difference in group means, and two-sided p-values will be reported.

A plot of all self-report survey results for each individual participant throughout the study will be provided. Pseudo-R code for the plot is included in Exhibit 6. Observations should be sorted first by the highest study day where the survey was filled out and then by the number of use days.

Exhibit 6 Pseudo-R Code for Survey Data Plot

```
par(mfrow=c(2,1))
par(mar=c(3,4,2,1))
plot(NA,NA,xlim=c(0,175),ylim=c(0,25),xlab=",
    ylab='Placebo Participant',
    main='Meth Survey Responses for Individual Subjects',yaxt='n',xaxt='n')
axis(1, at=seq(0, 175, by=7))
axis(2, at=seq(0,25,by=5))

for(i in 0:15){
    polygon(c(14*i+.5,14*i+7.5,14*i+7.5,14*i+.5), c(-5,-5,75,75),col=rgb(0,0,0,0.025),border=rgb(0,0,0,0.025))
}
```

points(nodrug_placebo\$DAY,nodrug_placebo\$SUBJIDN,col=rgb(0.2,0.7,0.9,1),pch=17,cex=1,yaxt='n') points(drug_placebo\$DAY,drug_placebo\$SUBJIDN,col=rgb(1,0.5,0,1),pch=19,cex=1)

Sequential weeks of abstinence from the end of treatment visit (Week 25)

An exploratory objective is to evaluate the efficacy of IXT-m200 in improving the length of sustained abstinence. Sequential weeks of abstinence counting backwards from the end of treatment visit (Week 25), defined as four weeks after the final planned treatment visit (Week 21), as measured by saliva screens in each IXT-m200 group will be compared to the placebo group. In the event there is no Week 25 visit, then the endpoint is counted from four weeks after the last dosing visit attended.

A "use day" or "abstinent day" will be derived as described for the primary endpoint. For each participant, sequential weeks abstinent counting backwards from the Week 25 visit will be calculated based on use/abstinent days, for a minimum of 0 weeks and maximum of 24 weeks of abstinence. Participants that withdraw or discontinue prior to Week 5, or do not have any reported saliva screen data between Weeks 5 and 25 will not be included in the analysis.

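### Percent days abstinent is tested with an unstratified t-test although randomisation is stratified by past-month METH use: valid, but conservative to the extent that the stratum predicts the outcome

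*SAP*

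**What the plan says.** Protocol section 6.3 says: "Randomization will be stratified by self-reported past-month METH usage at screening". The factor has two levels, fewer than 18 days and 18 or more.

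For percent of days abstinent by self-report between Week 5 and Week 25, SAP section 4.8 says: "The difference in percentage of days abstinent from stimulants will be compared in each IXT-m200 group versus the placebo group using a t-test". It names no stratum or covariate and gives no reason. The same section repeats the analysis without imputation of missing survey days, so both versions use the t-test.

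Elsewhere the SAP uses the factor:
- The primary ANCOVA (section 4.6.1) has as its second independent variable "Stratification level of past-month METH use at screening (discrete").
- The ANCOVA for sequential weeks of abstinence and the mixed model for point-prevalence abstinence (section 4.8) include it.
- The Mantel-Haenszel analyses of early remission at Week 25 (section 4.7.1.2), early remission at Week 33 and complete abstinence in Weeks 21 to 25 (section 4.8) are stratified by it.

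The Kruskal-Wallis tests for TEA, CGIC and PGIC (section 4.7.1.2) are also unstratified.

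On status, Table 3 and the section 4.8 heading make percent days abstinent exploratory, although its own paragraph calls the objective secondary. It is not among the endpoints in Protocol section 3.

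**The concern.** Stratified allocation balances the arms on past-month use. The true variance of the difference in means therefore excludes the part of the outcome variance that lies between strata. A two-sample t-test estimates its standard error from the total within-arm variance, which still contains that part. If past-month use predicts later abstinence, the standard error is too large on average.

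What is at stake is precision in a small trial. SAP section 1.2 records: "The study was stopped before enrolling Cohort 2". That leaves about 40 versus 20 participants. SAP section 4.1 also says the range of endpoints is meant to show how useful each one is for measuring treatment effect. If the saliva endpoint has a stratum-adjusted standard error and the self-report endpoint does not, part of any difference in their precision comes from the model and not from the endpoint.

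**Working it through.** **Inputs from the documents.** 2:1 allocation, about 40 versus 20 (SAP 1.2); two-sided nominal 5% (SAP 4.1.1); detectable difference of 0.78 pooled SD at 80% power for 40 versus 20 (SAP Table 4). On the basis of that table the SAP says: "The detectable differences were calculated in SAS Proc Power using a two-sample t-test assuming equal variance a two-sided 5% alpha". Table 4 was built for percent weeks; no figure is given for percent days.

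**Assumptions.** R² is the share of within-arm outcome variance explained by the two-level stratum, taken from 0 to 30%. For the simulation: blocks of 6 within strata, half or 70% of participants in one stratum, normal outcomes and a pooled-variance t-test. The documents give none of these.

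**Step 1: reproduce Table 4.** With a noncentral t on 58 df and SE = √(1/40 + 1/20) = 0.2739 SD, the detectable differences at 80%, 85% and 90% power are 0.780, 0.835 and 0.903 SD. The SAP states 0.78, 0.84 and 0.90, so the table is reproduced. Its 80% is the power of the unadjusted t-test.

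**Step 2: formulas.** Let w = √(1 − R²).
- True alpha of the t-test ≈ 2·[1 − Φ(1.96/w)].
- ANCOVA power: noncentral t on 57 df with noncentrality 0.78/(0.2739·w).
- Expected ANCOVA interval width relative to the t-test ≈ w.
- Gap between two equal-sized strata that yields a given R²: 2√R² in SD units.

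Example, R² = 10%: w = 0.949. Then 1.96/0.949 = 2.066, so alpha ≈ 3.9%. Noncentrality is 2.848/0.949 = 3.00, so ANCOVA power is 83.9%.

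**Step 3: results.** Simulations of 60 participants used 10,000 to 20,000 trials per setting.

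| R² | Gap between strata (SD) | t-test alpha, formula | t-test alpha, simulated | t-test power at 0.78 SD, simulated | ANCOVA power, formula | Width ratio w |
|---|---|---|---|---|---|---|
| 0 | 0 | 5.0% | 4.9–5.0% | 80% | 80% | 1.00 |
| 5% | 0.45 | 4.4% | 4.2–4.8% | 80–81% | 82% | 0.97 |
| 10% | 0.63 | 3.9% | 3.8–3.9% | 81% | 84% | 0.95 |
| 20% | 0.89 | 2.8% | 2.8–3.3% | 82–83% | 88% | 0.89 |
| 30% | 1.10 | 1.9% | 1.9–2.3% | 83–84% | 92% | 0.84 |

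Simulated ANCOVA alpha stays at 4.8–5.4%, and its simulated power agrees with the formula to within about half a point. The t-test gives up nothing at R² = 0, about 1 to 2 points at 5%, 3 at 10%, 5 to 6 at 20% and 8 at 30%.

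**The case against.** The strongest reply is that the size is unknown and may be negligible. No document says how well past-month use predicts percent days abstinent. With equal strata, R² of 20% or 30% needs the strata to differ by 0.89 or 1.10 SD, more than the 0.78 SD treatment effect in Table 4. Counting missing survey days as use could weaken the association further. This stands, and it is why the range starts at zero.

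It is also fair that little depends on this test. P-values are nominal, there is no multiplicity adjustment, and SAP section 2.2 says the sample size was not set to detect a particular effect. TEA, CGIC and PGIC, which rank higher in the SAP, are unstratified too. However, those are ordinal scales tested by ranks, and the SAP explains the nonparametric choice for TEA. Percent days abstinent is the only formally tested abstinence endpoint without the stratum, and no reason is given.

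Three stronger readings are tempting, and the documents do not support them:

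- **That power falls below 80%.** If the effect is set so that ANCOVA has 80% power, the t-test has 1 − Φ((1.96 − 2.80w)/w), which is 77%, 73% and 68% at R² of 10%, 20% and 30%. The arithmetic is right, but the effect then shrinks from 0.78 to about 0.74, 0.70 and 0.65 SD. The SAP's 80% belongs to the unadjusted t-test at 0.78 SD, and at that effect the t-test does not drop below about 80%. The loss is relative to ANCOVA.
- **That the saliva and self-report results cannot be compared because only one is adjusted.** Under stratified randomisation, adjusted and unadjusted analyses of an endpoint target the same difference in means; only precision differs. The two endpoints differ far more by design: saliva versus self-report, weeks versus days, and a missed screen failing a whole week versus a missing survey failing one day.
- **That the test is invalid.** The error is in the conservative direction, so there is no added false-positive risk from this source.

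**Conclusion.** The point holds as a minor matter of efficiency and consistency. When the stratum is prognostic, the t-test for percent days abstinent is valid but conservative. Within the assumed R² range of 0 to 30%, its true alpha lies between 5% and about 2%, and it loses between 0 and about 8 power points to ANCOVA at the Table 4 effect. At R² of 5% or less the loss is under 2 points.

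The direction follows from stratified allocation and does not depend on the assumed values. The size does: it rests on R², and the simulated figures also on block size, stratum split, normal outcomes, pooled variance and the planned 40 versus 20. The estimated quantity and the primary conclusion do not change.

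**What to change.** In SAP section 4.8, replace the t-test for percent days abstinent with the model of section 4.6.1: ANCOVA with treatment group and the past-month METH-use stratum as independent variables. Report the adjusted difference, 95% confidence interval and two-sided p-value for both the imputed and the non-imputed version. The t-test may stay as a supportive analysis.

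The cost is one line of SAP text, code that the primary endpoint already needs, and one residual degree of freedom (57 instead of 58). If the stratum explains nothing, power is unchanged to within a tenth of a point. SAP section 1 provides for changes to planned methods by amendment before database lock, and allows further exploratory or supportive analyses to be described in the study report without one. The ANCOVA can therefore be added by either route; making it the planned analysis before lock is the cleaner one.

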4 STUDY DESIGN

4.1 OVERALL DESIGN

A Phase 2 double-blind, randomized, placebo-controlled, multiple-dose study will be performed to evaluate the safety and efficacy of IXT-m200 in treatment-seeking individuals who use METH. The hypotheses are that following an initial relapse, IXT-m200 will reduce the occurrence of stimulant-positive saliva samples compared to placebo and improve the signs and symptoms of MUD.

Approximately 120 participants will be randomized in two sequential cohorts. In Cohort 1, approximately 60 participants will be randomized 2:1 to IXT-m200 at 1.5 g or placebo, with approximately 40 individuals receiving treatment and approximately 20 individuals receiving placebo. An interim analysis of data collected through Week 25 will be performed between cohorts to review efficacy data and to determine the need for dose escalation. If the interim analysis supports dose escalation, then Cohort 2 will randomize approximately 60 participants 2:1 to IXT-m200 at 3 g or placebo. If the interim analysis supports dose maintenance or reduction, however, then the sample size for Cohort 2 will be recalculated. Randomization will be stratified by self-reported past month METH usage at screening (<18 days per month versus ≥ 18 days per month).

Approximately 18 participants of the 60 per cohort will be enrolled in the PK subset. This subset will consist of approximately 12 active and 6 placebo participants in each cohort. Additional PK samples will be taken after the first and last doses in order to determine the effect of multiple doses on antibody PK. If 18 participants have not been enrolled in the PK subset by the time a cohort is filled, the Sponsor will determine if additional enrollment is required.

Each participant will receive 6 doses given by IV infusion, with doses given every 4 weeks. Participants will also receive concurrent cognitive behavioral therapy during monthly sessions. Saliva drug tests will be conducted randomly, with each participant completing two tests each week.

The first four weeks of treatment will be considered a grace period, designed to accommodate the likelihood that participants will relapse initially and experience the effects of IXT-m200. It further allows participants time to absorb and incorporate some of the skills taught by cognitive behavior therapy. METH use endpoints will be analyzed in the weeks following the grace period.

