8.1.2 SALIVA DRUG SCREENS

- Qualitative saliva drug screens will be used during screening and twice weekly throughout the study (Weeks 1-32) to screen for substances of abuse including amphetamine, cocaine, methamphetamine, and opiates. Saliva testing will be strictly monitored by performance of a specific series of steps recorded by video and reviewed by a trained professional to ensure validity of the test results.

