8.1.3 SELF-REPORT OF DRUG USE VIA APP

- Participants will be required to install an app on their smartphone, tablet, or similar device which records daily self-reported drug use from Day 1 through Week 32 or the Early Termination visit. The app will query participants daily on their past-day use, upload responses to a database at regular intervals, and notify investigators when participants are non-responsive.

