4.1.5. Definition of Study Time Points

Baseline is the latest pre-dose assessment with a non-missing value on or before the date of randomization (Day 1). If time is not collected, Day 1 assessments are assumed to be taken prior to first dose and used as baseline. If baseline data are missing, no derivation will be performed, and baseline will be set to missing.

The following conversion factors will be used to convert days to weeks, months, and years: 1 week = 7 days, 1 month = 30.4375 days, and 1 year = 365.25 days.

For all randomized participants, Day 1 is the date of randomization. Day 1 is the planned timepoint for the first dose administration. Day 1 is also the start of "Week 1".

For assessments on or after the randomization date, time is calculated in days as:

Study Day = Assessment Date - Randomization Date + 1 (positive number)

For assessments prior to the randomization date, time is calculated in days as:

Study Day = Assessment Date – Randomization Date

For other time variables based on two dates, Duration (days) = End Date - Start Date + 1.

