The difference between each IXT-m200 group and the placebo group in sequential weeks of abstinence counting backward from Week 25 will be estimated using an ANCOVA model. The independent variables in the model will be treatment group and stratification level of past-month METH use at screening. Adjusted means and standard errors for each treatment group and the estimated difference between the groups and associated 95% confidence intervals and two-sided p-values will be reported. Figures and tables will summarize the outcomes and analysis results.

This analysis will be repeated with the PP population.

Point prevalence abstinence (last 7 days)

One exploratory objective is to evaluate the efficacy of IXT-m200 in improving post-treatment abstinence. Point prevalence abstinence (last 7 days) by saliva screens at Week 25, Week 29, and Week 33 will be compared between each IXT-m200 group and the placebo group.

For each visit of interest, abstinence or use will be based on the saliva screens in the previous seven days. A "use day" or "abstinent day" will be derived as described for the primary endpoint. A participant will be categorized as fully abstinent if their saliva screens are negative (responder); a participant will be categorized as not abstinent if any of their saliva screens are positive (failure). The generalized linear mixed model assumes that data are missing at random.

A generalized linear mixed model regressing binary abstinence on treatment group, visit, stratification level of past-month METH use at screening, and a treatment group by visit interaction term. For each comparison, the odds ratio, 95% confidence interval, and two-sided p-value will be reported. Figures and tables will summarize the outcomes and analysis results. Within-subject correlations will be modeled using an unstructured covariance structure. If the model does not converge (i.e., the study has too few observations for the number of parameters estimated), the model will sequentially use the heterogeneous Toeplitz structure, homogeneous Toeplitz structure, or compound symmetry structure, each requiring successively fewer parameters.

Complete abstinence between Week 21 and Week 25 responder analysis

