4.9.1. PK Sampling Schedule

Section 1.3.2 of the protocol contains the full participant schedule for the PK subset.

- In all main study subjects, blood samples will be taken for analysis of IXT-m200 in serum on Day 1, Day 29, Day 57, Day 85, Day 113, and Day 141 at pre-dose (≤30 min prior) and 4 hours (±10 min) after the start of dosing, and once each visit on Day 169, Day 197, Day 225, and at early termination.
- In subjects in the PK subset, blood samples will be taken for analysis of IXT-m200 in serum on Day 1 and Day 141 at pre-dose (≤30 min prior), 1 hour (±10 min) and 4 hours (±10 min) after the start of dosing, and once at each visit on Day 2, Day 8, Day 15, Day 22, Day 142, Day 148, Day 155, and Day 162. Blood samples will also be taken at pre-dose and 4 hours after the start of dosing on Day 29, Day 57, Day 85, and Day 113, and once each visit on Day 169, Day 197, Day 225, and at early termination.

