5.1. Appendix 1: Schedule of Events

Assessment a	Screening	Dosing (-2/+7 days)				Follow-up (±3 days)			ET		
Study Week	≤-1	1	5	9	13	17	21	25	29	33	NA
Study Day	-60 to -1	1 ^b	29	57	85	113	141	169	197	225	NA
Informed consent	X										
Initial evaluations											
Eligibility criteria											
Demographics											
Medical history and medications	X										
Vital signs ^c	Α										
Physical and psychiatric exam											
Urine pregnancy test											
Saliva drug screen											
Laboratory tests d	X	X	X	X	X	X	X	X			X
Electrocardiogram (ECG) e	X	X	X	X	X	X	X				
App training											
App download and tutorial	X										
Saliva drug screens until acceptable											
Quality of Life Assessments f	X				X			X		X	X
Methamphetamine Use Assessments	X							X		X	X
Randomization		X									
Blood for PK/HACA & Cytokines g		X	X	X	X	X	X	X	X	X	X
Dose administration h		X	X	X	X	X	X				
Cognitive behavioral therapy		X	X	X	X	X	X		X		
Wellness check											
Update medical history											
Update medications											
Brief psychiatric evaluation		X	X	X	X	X	X	X	X	X	X
Vital signs ^c											
Targeted physical exam											
Urine pregnancy test											
Continuous events											
AE monitoring i											
Recovery coaching j						Con	tinuous				
Self-report daily drug use by app											
Random saliva drug screens k	14.64 1		1		11 >			1.1 DI		1.	

Abbreviations: ET - early termination; HACA - human anti-chimeric antibodies; NA - not applicable; PK - pharmacokinetic

^a Descriptions of assessments are in Section 8.1 (efficacy) or 8.2 (safety).

^b Study Day -1 is the day prior to the first dose. Study Day 1 is the day of the first dose.

^c Vital sign measurements will be taken on dosing days starting with a pre-dose measurement (≤30 min prior), then 0.25, 0.5, 1, 2, and 4 hours (±5 min) after dosing starts, and as needed afterward until normalization. Measurements will be obtained once on each non-dosing day. Each test may be repeated once at each time point if the initial result is out of range.

^d Laboratory tests require blood and urine sampling for hematology, serum chemistry, and urinalysis. Samples are to be taken 2-hr post-dose completion (±10 min) on dose days.

^e ECGs are to be done 30-min post dose completion (±15 min) on dosing days.

f Quality of Life Assessments include TEA, PGIC, and CGIC.

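### Week 33 point-prevalence abstinence looks back seven days from a visit that can fall after saliva screening has ended, so it is not measured on the same basis as Weeks 25 and 29

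*SAP*

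**What the plan says.** SAP 4.8 (point prevalence abstinence) covers Weeks 25, 29 and 33: "For each visit of interest, abstinence or use will be based on the saliva screens in the previous seven days". A participant whose screens in that window are negative is a responder, and any positive screen makes a failure. No minimum number of screens is given. The analysis is a generalized linear mixed model with treatment, visit, stratum and treatment-by-visit terms, assuming data are missing at random.

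Screening is random within the week: "Saliva drug tests will be conducted randomly, with each participant completing two tests each week" (Protocol 4.1). Protocol 8.1.2 schedules it "twice weekly throughout the study (Weeks 1-32"). Self-report also stops then, running "from Day 1 through Week 32 or the Early Termination visit" (Protocol 8.1.3), so it could not fill a gap after Week 32.

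SAP 4.1.5 makes Day 1 the start of Week 1. The nominal visits are Days 169, 197 and 225 (SAP 4.9.1), each with a window of 3 days either way (SAP Appendix 1 and the protocol schedules).

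Three statements bear on absent screens. SAP 4.8 assumes missing at random. SAP 4.1.2 scores missing responder values as non-response. SAP 4.6.1 counts a week with a missed screen as not abstinent, and 4.8 takes its use-day derivation from the primary endpoint. None says whether a screen that was never scheduled counts as missed.

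**The concern.** The look-back window is tied to the actual visit, while screening stops at a fixed week. At Weeks 25 and 29 screening continues past the visit, so all seven preceding days are open to testing on any permitted visit day. At Week 33 a late visit pushes part of the window beyond the last screen.

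Week 33 is the last read-out for the post-treatment abstinence objective. The visit and treatment-by-visit terms would read a change in the amount of testing as a change in abstinence. SAP 4.1 also says the trial is meant to show how useful each endpoint is, and an endpoint whose sensitivity depends on the attendance date serves that aim poorly.

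**Working it through.** **Calendar.** The first day of study week w is 7 × (w − 1) + 1. For w = 25, 29 and 33 this gives Days 169, 197 and 225, matching the SAP. Week 32 is Days 218 to 224.

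**Covered days.** For a visit on Day v the window is Days v − 7 to v − 1, and only days up to 224 can carry a screen. Up to Day 225 all 7 days are covered. For Days 226, 227 and 228 the count is 6, 5 and 4.

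**Number of screens.** Assume two screens on distinct random days of each study week. With c covered days of Week 32, expected screens = 2c/7, and P(no screen) = C(7 − c, 2)/C(7, 2), where C(7, 2) = 21.

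| Week 33 visit | Covered days | Expected screens | P(no screen) |
|---|---|---|---|
| Day 225 | 7 | 2.00 | 0 |
| Day 226 | 6 | 12/7 = 1.71 | 0 |
| Day 227 | 5 | 10/7 = 1.43 | 1/21 = 4.8% |
| Day 228 | 4 | 8/7 = 1.14 | 3/21 = 14.3% |

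At Weeks 25 and 29 the expected number is 2.00 on every permitted visit day. The actual number can still range from 0 to 4 when the visit is 2 or 3 days off its nominal day, because the window then straddles two study weeks.

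**Effect on the proportion abstinent.** Let q be the chance that a screen is negative. The documents give no value, so 0.5, 0.7 and 0.9 are used as a range. Assume independent screens and visits spread evenly from −3 to +3 days. P(abstinent) is then the sum over k of P(k screens) × q^k, adjusted for how low counts are scored. Entries are Week 33 versus Week 29 (Week 25 is identical), in percent, with the difference in points.

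| Scoring rule | q = 0.5 | q = 0.7 | q = 0.9 |
|---|---|---|---|
| No screen = missing | 31.3 v 27.2 (+4.1) | 53.8 v 49.8 (+4.0) | 82.8 v 80.9 (+1.9) |
| No screen = non-responder | 29.9 v 26.7 (+3.2) | 51.6 v 48.9 (+2.7) | 79.7 v 79.4 (+0.3) |
| Fewer than two screens = failure | 15.4 v 16.7 (−1.3) | 31.3 v 34.9 (−3.6) | 53.6 v 61.5 (−7.9) |

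Scoring a participant with no screen as abstinent would give 33.6 v 28.5 (+5.1) at q = 0.5, but nothing in the SAP supports that rule.

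For Day 228 visits alone, against a Week 29 visit 3 days late, at q = 0.5: 41.7% v 27.4% (no screen missing), 35.7% v 26.3% (non-responder), 7.1% v 14.0% (fewer than two is a failure). Under the non-responder rule the Day 228 difference turns negative from about q = 0.86.

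**Effect on a treatment contrast.** Take q = 0.7 in one arm and 0.5 in the other, with the same visit timing and no screen treated as missing. The difference is 53.8 − 31.3 = 22.5 points at Week 33 and 49.8 − 27.2 = 22.6 at Week 29. The odds ratios are about 2.6 and 2.7.

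**The case against.** A reader might infer that Week 33 abstinence is inflated by construction, since fewer screens make an easier pass. The documents do not support that. It holds if only the available screens are judged. If the missed-screen rule of SAP 4.6.1 is applied to screens that were never scheduled, the sign reverses. Counting those as missed would fail participants because the protocol had stopped testing them, which seems an unlikely intention, but the SAP does not exclude it.

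A reader might also infer a biased treatment comparison. The same rule applies to both blinded arms, 4.8 plans no test of Week 33 against an earlier visit, and with equal timing in the two arms the contrast above barely moves. Bias would need differential lateness, of which there is no evidence.

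The sizes are also limited. Independent screens are the worst case, and correlated screens shrink the inflation. Visits on time or early lose nothing. SAP 4.1.2 scores days after withdrawal as not abstinent, so withdrawn participants are unaffected: at the 50% dropout the documents allow for, +4.1 among retained participants becomes 0.5 × 4.1 = about +2 in the full set.

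Finally, Day 224 is inferred. Protocol 8.1.2 names weeks, not days, the schedules list screening as continuous, and Protocol 9.4.2 works in visit weeks following the actual Week 5 visit. If Week 32 were taken to end at the actual Week 33 visit, the gap would close. SAP 4.1.5 favours the Day 1 count, but neither document states the day on which screening stops.

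All of this limits the consequence. The mismatch between the window and the Day 1 calendar remains.

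**Conclusion.** The point holds as a comparability problem. Counting weeks from Day 1, a Week 33 visit on Days 226-228 loses 1 to 3 of its 7 window days and up to 43% of its expected screens (1 − 1.14/2.00), which cannot occur at Weeks 25 or 29. Under the stated assumptions the shift among retained participants lies between about −8 and +4 points, and its sign depends on a scoring rule the SAP leaves open. The harm is to comparison across visits and to precision; no bias between arms is shown. As the endpoint is exploratory and p-values are nominal, this is a cheap improvement and does not threaten the trial's conclusions.

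**What to change.** In SAP 4.8, define the three point-prevalence windows as the complete study weeks before the nominal visits: Days 162-168 for Week 25, 190-196 for Week 29 and 218-224 for Week 33, whatever the actual visit date. At minimum do this for Week 33. Handle a missed assigned screen within that week by the primary-endpoint rule of SAP 4.6.1, and reconcile the missing-at-random sentence in 4.8 with that choice.

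Every retained participant then has one full study week with two assigned screens at each time point. Changing all three windows, although Weeks 25 and 29 are already covered, also removes the 0-to-4 spread in screen counts there.

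The cost is one sentence or so, with no new data. SAP Section 1 provides for amendment before database lock; after lock the change would be documented in the clinical study report. The downside is that the window may end a few days from the actual visit.
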